6.4.2 Contraindications, Warnings, and Precautions

For study drugs other than acalabrutinib, please refer to the respective US prescribing information.

6.4.2.1 Obinutuzumab

Contraindications

Obinutuzumab is contraindicated in subjects with known hypersensitivity reactions (e.g., anaphylaxis) to obinutuzumab or to any of the excipients, or serum sickness with prior obinutuzumab use.

Warnings and Precautions

- Infusion-related Reactions: IRR were the most frequently observed adverse drug reactions in subjects receiving obinutuzumab and occurred predominantly during infusion of the first **CCI** [REDACTED] IRR may be related to cytokine release syndrome, which has also been reported in obinutuzumab-treated subjects. In the majority of subjects, IRRs were mild to moderate and could be managed by slowing or temporary halting of the first infusion, but severe and life-threatening IRRs have also been reported. Mitigation measures to reduce IRRs should be followed (see local prescribing information and [Section 7.2.2](#)).

Patients must not receive further obinutuzumab infusions if they experience:

- Acute life-threatening respiratory symptoms,
- Grade 4 (i.e., life-threatening) IRR or,
- Second occurrence of a Grade 3 (prolonged/recurrent) IRR (after resuming the first infusion or during a subsequent infusion).

Subjects who have pre-existing cardiac or pulmonary conditions should be monitored carefully throughout the infusion and post-infusion period. Since hypotension may occur, withholding of antihypertensive treatments should be considered for 12 hours before and throughout each obinutuzumab infusion and for the first hour after administration.

- Hypersensitivity Reactions: Hypersensitivity reactions with immediate (e.g., anaphylaxis) and delayed onset (e.g., serum sickness) have been reported in subjects treated with obinutuzumab and may be difficult to clinically distinguish from IRRs. However, hypersensitivity very rarely occurs with the first infusion and, when observed, often occurs after previous exposure. If a hypersensitivity reaction is suspected during or after an infusion, the infusion must be stopped, and treatment permanently discontinued. Subjects with known hypersensitivity to obinutuzumab are not eligible for enrollment in this study.
- Tumor Lysis Syndrome: TLS has been reported with obinutuzumab. Subjects who are considered to be at risk of TLS (e.g., subjects with a high tumor burden and/or a high circulating lymphocyte count [$>25 \times 10^9/L$] and/or renal impairment [$\text{CrCl} < 70 \text{ mL/min}$]) should receive prophylaxis as described in the obinutuzumab prescribing information. Mitigation measures to reduce risk of TLS should be followed (see local prescribing information and [Section 7.1.1](#)).
- Neutropenia: Severe and life-threatening neutropenia, including febrile neutropenia, has been reported during treatment with obinutuzumab. Refer to [Section 7.1.1](#) and local

prescribing information for dose modification and discontinuation guidance. Supportive measures for any signs of infection should be considered. Subjects with renal impairment ($\text{CrCl} < 50 \text{ mL/min}$) are more at risk of neutropenia.

- Thrombocytopenia: Severe and life-threatening thrombocytopenia, including acute thrombocytopenia (occurring within 24 hours after the infusion), has been observed during treatment with obinutuzumab. Fatal hemorrhagic events have also been reported in Cycle 1 in subjects treated with obinutuzumab. A clear relationship between thrombocytopenia and hemorrhagic events has not been established.
- Worsening of Pre-existing Cardiac Conditions: Worsening of pre-existing cardiac conditions has been reported with obinutuzumab. In subjects with underlying cardiac disease, arrhythmias (such as atrial fibrillation and tachyarrhythmia), angina pectoris, acute coronary syndrome, myocardial infarction, and heart failure have occurred when treated with obinutuzumab. These events may occur as part of an IRR and can be fatal. Therefore, subjects with a history of cardiac disease should be monitored closely.
- Infections, Including HBV and PML: Obinutuzumab should not be administered in the presence of an active infection, and caution should be exercised when considering the use of obinutuzumab in subjects with a history of recurring or chronic infections. Fatal infections have been reported.

HBV reactivation, in some cases resulting in fulminant hepatitis, hepatic failure, and death, can occur in subjects treated with anti-CD20 antibodies including obinutuzumab. Refer to [Section 6.4.5](#) for additional information and monitoring guidance for viral hepatitis.

PML has been reported in subjects treated with obinutuzumab. Refer to [Section 6.4.6](#) for additional information and management guidance for signs and symptoms of PML.

Obinutuzumab should be withheld during the investigation of potential PML and permanently discontinued in case of confirmed PML.

- Immunizations: The safety of immunization with live or attenuated viral vaccines following obinutuzumab therapy has not been studied and vaccination with live virus vaccines is not recommended during treatment and until B-cell recovery.

6.4.2.2 Venetoclax

Contraindications

Concomitant use of venetoclax with strong CYP3A inhibitors at initiation and during the ramp-up phase is contraindicated.

Warnings and Precautions

- TLS: TLS, including fatal events and renal-failure requiring dialysis, has occurred in previously treated patients with CLL and high tumor burden when treated with venetoclax. Mitigation measures to reduce risk of TLS should be followed (see venetoclax prescribing information and [Section 5.3.2](#)).

- Drug interactions, including CYP3A: Although the risk of TLS is a continuum based on multiple factors, concomitant use of venetoclax with strong or moderate CYP3A inhibitors increases venetoclax exposure and may increase the risk for TLS at initiation and at the dose titration phase. Inhibitors of P-gp or breast cancer resistance protein (BCRP) may also increase venetoclax exposure. Additional information on venetoclax drug interactions is provided in [Section 6.3](#), and dose modification information is provided in [Section 7.1.2](#).
- Neutropenia: Grade 3 or 4 neutropenia has been reported in subjects treated with venetoclax. Refer to [Section 7.1.2](#) for local prescribing information for dose modification and discontinuation guidance. Supportive measures for any signs of infection should be considered.
- Immunization: Do not administer live attenuated vaccines prior to, during, or after venetoclax treatment until B-cell recovery occurs. The safety and efficacy of immunization with live attenuated vaccines during or following venetoclax therapy have not been studied.
- Embryofetal toxicity: Based on its mechanism of action and findings in animals, venetoclax may cause embryofetal harm when administered to a pregnant woman. Refer to [Section 6.4.3](#) for additional reproductive toxicity information and contraception guidance.

6.4.2.3 Rituximab

- TLS: Administer aggressive IV hydration, antihyperuricemic agents, and monitor renal function.
- Infections: Withhold rituximab and institute appropriate anti-infective therapy.
- Cardiac arrhythmias and angina: Discontinue infusions in case of serious or life-threatening events.
- Bowel obstruction and perforation: Consider and evaluate for abdominal pain, vomiting, or related symptoms.
- Live virus vaccines: Do not administer live virus vaccines prior to or during rituximab.
- Cytopenias: Monitor blood counts at regular intervals.
- Infusion reactions: Rituximab administration can result in serious, including fatal infusion reactions. Deaths within 24 hours of rituximab infusion have occurred. Approximately 80% of fatal infusion reactions occurred in association with the first infusion. Monitor patients closely. Discontinue rituximab infusion for severe reactions and provide medical treatment for Grade 3 or 4 infusion reactions.
- Severe mucocutaneous reactions: Severe, including fatal, mucocutaneous reactions can occur in patients receiving rituximab.
- HBV reactivation: HBV reactivation can occur in patients treated with rituximab, in some cases resulting in fulminant hepatitis, hepatic failure, and death. Screen all patients

for HBV infection before treatment initiation and monitor patients during and after treatment with rituximab. Discontinue rituximab and concomitant medications in the event of HBV reactivation. Any subject with a rising viral load (above lower limit of detection) should discontinue study drug, have antiviral therapy instituted, and have a consultation with a physician with expertise in managing hepatitis B. Patients who are anti-HBc positive may receive prophylactic antiviral agents while undergoing CLL therapy, per institutional guidelines.

- PML, including fatal PML, can occur in patients receiving rituximab.

6.4.2.4 Immunizations

Do not administer live attenuated vaccines prior to, during, or after treatment with venetoclax, obinutuzumab, or rituximab until B-cell recovery occurs. The safety and efficacy of immunization with live attenuated vaccines during or following venetoclax therapy have not been studied. Advise subjects that vaccinations may be less effective.

Based on nonclinical data, no changes are recommended to standard of care practices with regard to vaccinations in subjects treated with acalabrutinib. As appropriate, vaccines consistent with standard practices for specific subject populations (e.g., patients with CLL) should be used.

6.4.2.5 Dietary Restrictions

As acalabrutinib is metabolized by CYP3A, subjects should be strongly cautioned against using herbal remedies or dietary supplements (in particular, St. John's wort, which is a potent CYP3A inducer). These restrictions also apply to venetoclax.

6.4.3 Reproductive Toxicity

Definition of women of nonreproductive potential:

Women will be considered of non-reproductive potential if they are either:

- (1) Postmenopausal (defined as at least 12 months with no menses without an alternative medical cause; in women <45 years of age a high follicle-stimulating hormone [FSH] level in the postmenopausal range may be used to confirm a postmenopausal state in women not using hormonal contraception or hormonal replacement therapy. In the absence of 12 months of amenorrhea, a single FSH measurement is insufficient.).

OR

- (2) Have had a hysterectomy and/or bilateral oophorectomy, bilateral salpingectomy, or bilateral tubal ligation/occlusion, at least 6 weeks prior to screening.

OR

- (3) Have a congenital or acquired condition that prevents childbearing.

Highly effective methods of contraception (to be used during heterosexual activity) are defined as methods that can achieve a failure rate of <1% per year when used consistently and correctly. Such methods include:

- Combined (estrogen and progestogen containing) hormonal contraception associated with inhibition of ovulation, which may be oral, intravaginal, or transdermal
- Progestogen-only hormonal contraception associated with inhibition of ovulation, which may be oral, injectable, or implantable
- Intrauterine device (IUD) or intrauterine hormone-releasing system (IUS)
- Bilateral tubal occlusion
- Vasectomy of a female subject's male partner (with medical assessment and confirmation of vasectomy surgical success)
- Sexual abstinence (only if refraining from heterosexual intercourse during entire period of risk associated with the study treatments)

Hormonal contraception may be susceptible to interaction with study or other drugs, which may reduce the efficacy of the contraception method.

Abstinence (relative to heterosexual activity) can only be used as the sole method of contraception if it is consistently employed during the entire period of risk associated with the study treatment as the subject's preferred and usual lifestyle.

Period abstinence (e.g., calendar, ovulation, symptom-thermal, and post-ovulation methods) and withdrawal (coitus interruptus), spermicides only, and lactational amenorrhea method (LAM) are not acceptable methods of contraception. Female condom and male condom should not be used together as an effective method of contraception.

Please refer to the acalabrutinib Investigator Brochure for information on reproductive toxicity studies.

Obinutuzumab is likely to cause fetal B cell depletion, although there are no data from the use of obinutuzumab in pregnant women to inform a drug-associated risk.

There are no adequate and well-controlled studies of rituximab in pregnant women. Women of childbearing potential should use effective contraception while receiving rituximab and for 12 months following treatment. Rituximab is a pregnancy class C drug.

There are no available human data on the use of venetoclax in pregnant women. Based on toxicity observed in mice, venetoclax may cause fetal harm when administered to pregnant women. In mice, venetoclax was fetotoxic at exposures 1.2 times the human clinical exposure

based on AUC at the recommended human dose of CCI. If venetoclax is used during pregnancy or if the patient becomes pregnant while taking venetoclax, the subject should be apprised of the potential risk to a fetus.

Women who are sexually active and can bear children (see definition above) must agree to use highly effective forms of contraception during the study and 30 days after the last dose of venetoclax, 2 days after the last dose of acalabrutinib, 12 months after the last dose of rituximab, or 18 months after the last dose of obinutuzumab, whichever is the longest period following the subject's study drug discontinuation. Men who are sexually active and are able to have children must agree to use highly effective forms of contraception and use a barrier method (condom, even if the subject had a vasectomy) during the study and for 18 months after the last dose of obinutuzumab, or 12 months after the last dose of rituximab, or 30 days after the last dose of venetoclax, whichever is longer. Men must also refrain from donating sperm during the study and for 18 months after the last dose of obinutuzumab, or 12 months after the last dose of rituximab, or 30 days after the last dose of venetoclax, whichever is longer.

Subjects should be informed that taking the study medication may involve unknown risks to the fetus (unborn baby) if pregnancy were to occur during the study. To participate in the study subjects of childbearing potential must adhere to the contraception requirement (described above) from the day of study medication initiation (or 14 days prior to the initiation of study medication for oral contraception) throughout the study period up to 2 days after the last dose of acalabrutinib or 18 months after the last dose of obinutuzumab, whichever is longer. If there is any question that a subject of childbearing potential will not reliably comply with the requirements for contraception, that subject should not be entered into the study. Subjects should promptly notify the investigator if they, or their partner, become pregnant during this period. If a female subject becomes pregnant during the treatment period, she must discontinue acalabrutinib immediately. Pregnancy in a female subject or a male subject's partner must be reported in the same manner as any serious adverse event (SAE). All pregnancies and partner pregnancies that are identified during or after this study, wherein the estimated date of conception is determined to have occurred from the time of consent to 2 days after the last dose of acalabrutinib or 18 months after the last dose of obinutuzumab (whichever is longer) will be reported, followed to conclusion, and the outcome reported, as long as the subject or partner is willing to participate in follow-up.

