9. Absolute neutrophil count (ANC) $\geq 750/\text{mm}^3$. In subjects with CLL involvement of the marrow, ANC $\geq 500/\text{mm}^3$. For Cohorts 3 and 4, subjects must have ANC $\geq 1000/\text{mm}^3$.
10. Subject must have an Eastern Cooperative Oncology Group (ECOG) performance status ≤ 2 .
11. Subject must not have secondary cancers that result in a life expectancy of <2 years or that would confound assessment of toxicity in this study.
12. Subjects must be ≥ 18 years of age.
13. Subject must provide written informed consent. A signed copy of the consent form will be retained in the subject's chart.

14. Subject must be able to receive outpatient treatment and follow-up at the treating institution.
15. Subject must have completed all CLL therapies ≥ 4 weeks prior to first study dose. Palliative steroids are allowed but must be at a dose equivalent of ≤ 20 mg prednisone daily for at least 1 week prior to treatment initiation.
16. Women who are sexually active and can bear children must agree to use highly effective forms of contraception while on the study and for 2 days after the last dose of acalabrutinib, 30 days after the last dose of venetoclax, 12 months the last dose of rituximab, or 18 months after the last dose of obinutuzumab, whichever is the longest period following the subject's study drug discontinuation. Men who are sexually active and able to have children must agree to use highly effective methods of contraception during the study and use a barrier method (condom; even if the subject had a vasectomy) for 2 days after the last dose of acalabrutinib, 18 months after the last dose of obinutuzumab, or 12 months after the last dose of rituximab, or 30 days after the last dose of venetoclax, whichever is longer. Highly effective forms of contraception are defined in [Section 6.4.3](#). Additionally, men must agree to refrain from sperm donation during the study and for 18 months after the last dose of obinutuzumab, or 12 months after the last dose of rituximab, or 30 days after the last dose of venetoclax, whichever is longer.
17. Subjects must be able to swallow whole capsules.

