6.1.2 Acalabrutinib Plus Venetoclax plus Rituximab or Obinutuzumab

In the acalabrutinib plus venetoclax plus rituximab or obinutuzumab Phase 1b portion of the study, 12 subjects with relapsed/refractory CLL and 12 subjects with treatment-naive CLL will be enrolled into Cohorts 3 and 4, respectively. Subjects in Cohort 3 will be treated with acalabrutinib, rituximab, and venetoclax. Subjects in Cohort 4 will be treated with acalabrutinib, obinutuzumab, and venetoclax. Based on the safety observed with the combination of ibrutinib, venetoclax, and obinutuzumab in an ongoing study ([Jones et al. 2016](#)), safety will be reviewed for the first 3 subjects who complete Cycle 3 in each cohort. The review will be repeated for additional subjects if needed. Unless a safety concern is identified (e.g., dose delays [REDACTED] cci [REDACTED] enrollment in Cohorts 3 and 4 will continue during the safety review until the desired number of subjects is reached. There are no DLTs defined for this portion of the study. See [Section 5](#) for study drugs and administration guidelines.

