6.7 Duration of Therapy

For Cohorts 1 and 2, acalabrutinib treatment can continue until the end of study for subjects without disease progression and who are tolerating therapy. The end of study is defined as 36 cycles after the last subject is enrolled to allow for long term follow-up beyond 36 cycles.

For Cohorts 3 and 4, protocol therapy with obinutuzumab or rituximab will continue for up to cc1 (until the end of cc1 in responding subjects. Subjects will discontinue venetoclax at the end of cc1. Treatment with acalabrutinib is continued until evidence of disease progression, toxicity, or end of study, whichever occurs first. Acalabrutinib; however, can be discontinued by investigator decision after cc1 in subjects with CR/CRi and/or negative MRD.

cc1

In Cohorts 1 and 2, subjects who achieve a bone marrow MRD-negative CR have the option to discontinue acalabrutinib.

Subjects who are still on treatment at the end of study and deriving clinical benefit from acalabrutinib monotherapy may continue treatment. At the time of the final data cutoff (DCO)

and database closure, subjects who remain in the study may be transitioned to a separate rollover study or remain within this study for continued access to study drug. Once all active subjects are eligible to continue to receive acalabrutinib and after database closure, this study will be considered closed. There will be no further data collection other than reporting of SAEs per [Section 10.5](#). Access within this study will enable continued treatment with visit assessments per standard of care, whereas the separate rollover study will enable treatment continuation with visit assessments and data collection per the rollover study protocol.

See [Section 7](#) for dose modifications and [Section 11](#) for criteria for removal from the study.

7 Dose Adjustments and Modifications

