7.1.3.3 Rituximab Dose Modification and Discontinuation

Dose modification of rituximab is not recommended; please refer to the RITUXAN® prescribing information and [Section 7.1.2](#) and [Section 7.2](#) for details. If rituximab is discontinued, subjects can continue acalabrutinib and venetoclax as outlined in the protocol. If acalabrutinib or venetoclax is discontinued, a subject may continue to receive rituximab up to the maximum number of infusions as outlined in the protocol.

The US Prescribing Information for rituximab will serve as Reference Safety Information (RSI) for this study to facilitate determination of expectedness or unexpectedness of AEs possibly associated with rituximab.

7.2 Dose Adjustment and Management of Toxicity for Phase 1b After **CCI** and Phase 1b Expansion Phase, and Phase 1b Venetoclax Cohorts

This section describes management of hematologic and nonhematologic toxicities for subjects in the Phase 1b dose-escalation portion after **CCI** subjects in Cohorts 1 and 2 in the Phase 1b expansion portion. This section also describes management of hematologic and nonhematologic toxicities in the Phase 1b portion wherein venetoclax is added during **CCI** (Cohorts 3 and 4).

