10.2 Monitoring of Adverse Events

After the signing of the Informed Consent Form (ICF) and prior to the first dose of study drug, all SAEs must be reported.

After the first dose of study drug, all AEs/SAEs, irrespective of attribution of causality, must be reported.

All AEs will be reported until 30 days after the last dose of study drug(s) or the start of a new anticancer therapy (whichever comes first). After this period, investigators should report SAEs or other AEs of concern that are believed to be related to prior treatment with study drug.

All SAEs that occur during the reporting period should be followed to resolution or until the investigator assesses the subject as stable, or the subject is lost to follow-up or withdraws consent. Resolution/stable means the subject has returned to baseline state of health or the investigator does not expect any further improvement or worsening of the event.

The events must be detailed to include diagnostic term, severity, causality in relationship to the study drug, duration, action taken and outcome. The descriptions and grading scales found in the NCI-CTCAE version 4.03 or higher will be utilized for AE reporting.

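### The pregnancy-reporting window in Protocol 6.4.3 leaves out rituximab and venetoclax, so in Cohort 3 it can close about 12 months before the protocol's own contraception period ends

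*Protocol*

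**What the plan says.** Protocol Section 6.4.3 gives the only dated rule for which pregnancies are reported, followed to conclusion and their outcome reported. It covers conceptions that "occurred from the time of consent to 2 days after the last dose of acalabrutinib or 18 months after the last dose of obinutuzumab" (the later date applies).

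An earlier sentence in the same paragraph asks subjects to keep to the contraception requirement "up to 2 days after the last dose of acalabrutinib or 18 months after the last dose of obinutuzumab, whichever is longer". Subjects are then told to notify the investigator of any pregnancy in that period.

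The paragraph before sets contraception by all four drugs. For women it is the longest of 30 days after venetoclax, 2 days after acalabrutinib, and "12 months after the last dose of rituximab, or 18 months after the last dose of obinutuzumab, whichever is the longest period". The periods for men also include rituximab and venetoclax. Inclusion criterion 16 (Section 3.1) names the same four drugs: 2 days after acalabrutinib, "30 days after the last dose of venetoclax, 12 months the last dose of rituximab, or 18 months after the last dose of obinutuzumab".

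Section 6.1.2 gives the regimen: "Subjects in Cohort 3 will be treated with acalabrutinib, rituximab, and venetoclax".

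**The concern.** Cohort 3 receives no obinutuzumab, so the obinutuzumab limb of the reporting clause never applies and the window reduces to acalabrutinib plus 2 days. The protocol nevertheless treats these subjects and their partners as at risk for 12 months after rituximab and 30 days after venetoclax. A site that follows the clause exactly need not report, or follow to outcome, a conception that falls after the 2-day cut-off but inside that risk period.

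The loss falls where information is scarce. Section 6.4.3 itself says there are no adequate, well-controlled studies of rituximab in pregnancy and no human data for venetoclax, which was fetotoxic in mice. Subjects who stop early for progression are also the ones for whom scheduled contact shrinks to survival status (Section 8.5), so an explicit rule matters most for them.

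**Working it through.** The plan gives no figure of its own here, so the check is date arithmetic on its stated periods.

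**Inputs**
- Reporting window, Cohort 3: last acalabrutinib dose + 2 days (Section 6.4.3, Section 6.1.2).
- Contraception period: the longest of acalabrutinib + 2 days, rituximab + 12 months and venetoclax + 30 days (Section 6.4.3, inclusion criterion 16).
- 12 months taken as 365 days.
- 28-day cycles, with C24D1 = Day 645 (SAP Appendix A).
- First rituximab no earlier than C2D1 = Day 29 (Protocol Section 13.2.2 places a sample then, before the anti-CD20 antibody).
- Elective acalabrutinib stop only after Cycle 24 (Protocol Table 12, footnote A).

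**Formula.** Let Gr be the last acalabrutinib day minus the last rituximab day, and Gv the last acalabrutinib day minus the last venetoclax day. Then

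shortfall = max(0, 365 − 2 − Gr, 30 − 2 − Gv) = max(0, 363 − Gr, 28 − Gv).

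**Rituximab term**

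| Gr (days) | Shortfall (days) |
|---|---|
| −28 (rituximab runs 28 days longer) | 391 |
| 0 (same-day stop) | 363 |
| 90 | 273 |
| 180 | 183 |
| 270 | 93 |
| 363 or more | 0 |

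**Venetoclax term.** Gv = 0 gives 28 days; Gv of 28 or more gives 0.

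**Worst case.** Twelve months is not a ceiling. Section 7.1.3.3 says that after acalabrutinib stops "a subject may continue to receive rituximab up to the maximum number of infusions as outlined in the protocol". The rituximab end date is redacted, so as an assumption take acalabrutinib stopped on Day 29 and the last rituximab dose between C5D1 (Day 113) and C9D1 (Day 225). The shortfall is then 363 + 84 = 447 days to 363 + 196 = 559 days, or 14.7 to 18.4 months at 30.4375 days per month.

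**Planned course.** Cycle 24 ends on Day 645 + 27 = 672. A stop that day leaves no rituximab shortfall if the last rituximab dose was on or before Day 672 − 363 = 309, which is C12D1.

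**Early stop.** Even a single rituximab dose on Day 29 leaves a shortfall unless acalabrutinib continues to Day 29 + 363 = 392.

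**The case against.** The strongest reply is that other text partly covers the gap. Section 6.4.3 also says, with no date limit, that pregnancy is reported as an SAE would be. Section 10.2 runs AE reporting to 30 days after the last study drug and has SAEs in that period followed to resolution. On that reading the 28-day venetoclax shortfall roughly disappears, and the same-day rituximab shortfall falls to 365 − 30 = 335 days. Beyond that window, Section 10.2 adds: "After this period, investigators should report SAEs or other AEs of concern that are believed to be related to prior treatment with study drug".

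This softens the point without removing it. The SAE sentence concerns how a pregnancy is reported and sets no conception dates; the dated clause does. The 30-day window closes sooner if new anticancer therapy starts. After it, reporting depends on judged relatedness, and nothing requires a later conception to be followed to outcome.

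The second reply is that the planned course probably has no gap. Under Section 6.7, "Treatment with acalabrutinib is continued until evidence of disease progression, toxicity, or end of study, whichever occurs first", and the elective stop comes only after Cycle 24. Table 12 lists visits through Cycle 7 and then every third cycle, which suggests, as an inference only, that rituximab ends by about C7D1 (Day 169). The gap would then vanish once acalabrutinib reached Day 169 + 363 = 532. That stands: the exposure is mainly early stopping for progression or toxicity.

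Third, reach is small: 12 planned subjects at one site, in a disease that Section 2.1 describes as having an average age at diagnosis of 72. Contraception itself is still governed by the four-drug rule, so the short adherence sentence is only an incomplete restatement. SAP Section 13.1 ends the treatment-emergent window at 30 days after the last dose, so no planned AE table changes. All of this limits the consequence; none of it makes the clause right.

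**Conclusion.** The concern holds. For Cohort 3 the reporting clause contradicts the risk period set one paragraph earlier. The shortfall is 363 days on a same-day stop of acalabrutinib and rituximab, more if rituximab outlasts acalabrutinib, and zero if acalabrutinib runs at least 363 days past the last rituximab dose. Allowing for the 30-day SAE window still leaves about 335 days on a same-day stop of all drugs. The venetoclax shortfall is at most 28 days when it and acalabrutinib stop together, and about zero if the 30-day window is read in.

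These figures rest on 28-day cycles and a 365-day year. The typical gap cannot be computed because the rituximab end date is redacted. It applies to Cohort 3 subjects of reproductive potential who stop acalabrutinib too soon after rituximab or venetoclax. Few events are expected, so this is a safety follow-up correction that should be made, with no bearing on the trial's inference.

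**What to change.** In both the adherence sentence and the reporting sentence of Section 6.4.3, add 12 months after the last rituximab dose and 30 days after the last venetoclax dose, and state that the longest period applies. Alternatively, replace the dates in both sentences with a cross-reference to the four-drug contraception period in the preceding paragraph, which avoids stating the dates twice. Either version brings the shortfall to zero in every cohort. The cost is two sentences in one section, with no change to sample size, power or analysis.
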